Exclusion criteria: Insufficient skills in Danish language and reduced mental function that prevents reading and answering the questionnaires. For the VO₂peak test: Motor complete SCI (AIS A and B) at C4 level or above and assisted ventilatory function. Other exclusion criteria are the presence of decubitus, severe spasticity or musculoskeletal problems considered at risk of aggravation during testing or preventing completion of the test.

Recruitment of participants:

All newly injured patients who are admitted for rehabilitation at CSCI during the project period are included in the intervention (subproject 2) as it becomes a part of usual care during the project period. The Ph.D student is informed about new and future admissions at CSCI by local patient lists every week, and LTPAQ-SCI, ESES, QoL_SCI and NORMON is handed out to the patient and collected again by the Ph.D student. Date and time for the VO₂peak test is handed to the patients physiotherapist, who will make sure to enter it into the patients weekly schedule. The same procedure is repeated at discharge except that QoL_SCI is collected as a part of existing procedures and PHQ-2 is collected by the Ph.D student. In subproject 1, data for VO₂peak at CSCI will only be collected at discharge. All newly injured patients who are admitted for rehabilitation at VCR in the same period are recruited for subproject 1 and data for BMI, SCIM III and ISNCSCI is collected as a part of existing procedures in usual care.

The coordination related to booking of the DEXA-scan and transportation for this is managed by the secretaries. Ordination of the DEXA-scan as well as blood samples related to metabolic profile is handled by the doctors.

Ethical considerations

During the intervention period all newly injured patients who are admitted for rehabilitation are offered the treatment and tests included in the intervention to the extent they are able to participate depending on eg. the level of lesion and completeness of the injury, as this is a part of usual care and will continue as a part of usual care after termination of the project. The regional ethical committee will be contacted to clarify the need to report sub project 2 while the intervention in the project is closely related with the content of the present rehabilitation, why the risk of pain and discomfort related to the elements in the intervention is considered modest. Patients who are re-hospitalized for control visit will not be a part of the project and will receive usual rehabilitation.

During the VO₂peak test, there will be special attention on symptoms of autonomic dysreflexia (AD) in people with SCI above T5-6. Several symptoms may be present and include a 20mm Hg increase in systolic blood pressure above baseline, headache, flushing and cold sweating above the level of injury. In this case the exercise test is disrupted and relevant actions are initiated, such as loosening of tight clothes, an upright positioning depending on the severity of AD. If the exercise test results in orthostatic hypotension (OH) the test is disrupted and the patient is placed in a horizontal position with elevation of the lower extremities above heart level.

Any unintended events related to the elements of the intervention is reported according to existing guidelines.

It is assumed that any risks is by far surpassed by the therapeutic gains such as an expected risk reduction of cardiovascular disease and consequently mortality.

Funding and organization

This work was supported by a mutual cooperation about the research program "Centre for Integrated Rehabilitation of Cancer Patients (CIRE) - Neuro/Psychology", between the University Hospitals Centre for Health Care Research (UCSF), University hospital Copenhagen, Rigshospitalet, [name] ([name]); the Metropolitan University College (Metropol), Institute for Nursing, the Health and Technological Faculty, [name] and the NeuroScience Centre, section 2091; Rigshospitalet, [name]; Neurologic department, Nordsjællands Hospital and Psychiatric centre, Glostrup Hospital.

The initiative behind the neuro/psyk programme consists of researchers and leaders from UCSF and Metropol, as well as the steering committee of UCSF consisting of representatives from the hospital directors in the Capital region (Vicedirector for University hospital Copenhagen, Rigshospitalet [name], hospitalsdirector for Nordsjællands hospital [name], vicedirector for the psykiatri in the capital region [name], and associate dekan Metropol [name]).

The project group in relation to the Ph.D projektet consist of senior researcher [name] (UCSF, head supervisor), professor [name] (Neuroscience centre Rigshospitalet, Clinic for Spinal Cord Injuries, co-supervisor), Docent [name] (Metropol, co- supervisor), professor [name] (UCSF), senior researcher [name] (UCSF), head nurse [name] (Clinic for Spinal Cord Injuries), leading therapist [name] (Clinic for Spinal Cord Injuries)

Clinic for Spinal Cord Injuries), clinical nurse specialist [name] (Clinic for Spinal Cord Injuries) and center manager nurse ([name] (Neuroscience centre, Rigshospitalet.

Interests of conflict

The Ph.D student has no interests of conflict related to the project in general or any of the subprojects

Risk assessment and changes to the protocol

The completion of the Ph.D project may come in danger if the intervention elements and workflows are not implemented by one or several of the interdisciplinary professions, or if the necessary data are not collected by the interdisciplinary professions. If this appears to be the case during collection of data from the patients journal in Epic or it is expressed by the staff at staff meetings, the responsible department managers will be informed in order to ensure the implementation of the elements.

The Ph.D project may also come in danger if the patients are engaged in other research projects parallel to the Ph.D project, which is considered to be most likely, but since the Ph.D project comprises the patients standard treatment, the risk that the patients participation in other research projects will affect the Ph.D project is considered modest. Also the Ph. D project may come in danger if the patients does not consent to the use of their data in the project.

A significant challenge to the project, and a factor able to impact on the projects completion is the logistic planning related to the patients having the necessary tests made at the right times at admission, discharge and follow up, for which they need to be called in for.

Some of the data used in project and many of the settings and work flows used in the intervention is a part of the existing settings and procedures, which is ensuring the completion of the project.

At Clinic for Spinal Cord Injuries the clinic management by head nurse [name], leading therapist [name] and head of the clinic [name] are responsible for ensuring the setting necessary for completing the project and its elements. At an overall level center manager nurse [name], Neuroscience centre, Rigshospitalet is responsible for ensuring the necessary setting for the completion of the project.

Changes to the protocol will be described in an additional protocol.

Publication of results:

Attempts will be made to publish the projects results in relevant scientific journal such as BMJ Open, Archives of Physical Rehabilitation Medicine, Journal of Spinal Cord Medicine and Spinal Cord. Listed below are the preliminary titles of the articles.

The Ph.D student will be primary author on all articles primary supervisor [name] will be last author on articles related to subproject 2, 3 and 4, while co- supervisors [name] and [name] are last authors on articles related to subproject 1 and the protocol article respectively. Clinical nurse specialist [name] is co- author on the protocol article and the article related to subproject 1

Protocol article: Health and Cardiovascular Risk Reduction in People with Spinal Cord Injury - Physical Activity, Healthy Diet and Adherence after Discharge from Primary Rehabilitation.

1. Longitudinal National Survey of Body Mass Index and Measures of Functional Recovery, Depression, Quality of life, Physical Activity and Exercise Self Efficacy during Inpatient Spinal Cord Injury Rehabilitation and Follow Up.
2. Effects of a Systematic and Interdisciplinary, Multimodal and Patient Engaging Intervention on , Metabolic Markers, Body Composition, Physical Activity and Diet, Quality of Life and Exercise Self Efficacy during Inpatient Rehabilitation with Follow up, Facilitating Adaptation to Physical Activity and Healthy Diet in People with Spinal Cord Injury.

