The prevalence of overweight among people with SCI is high and is conservatively estimated to 66% [4]. In a Swedish cohort of wheelchair dependent people with paraplegia, 27- 36% had a cardiovascular risk profile requiring treatment. When Body Mass Index (BMI) adjusted to SCI was entered into the risk model, 80% had a risk profile requiring treatment [5]. Energy expenditure decreases significantly the first weeks after injury and remains low throughout the primary rehabilitation, with the possibility of decreasing even more the following years. Body fat and body weight also decreases in the acute phase, before increasing in the subacute phase towards the same level as before the time of injury [6]. A longitudinal study with participants ranging from 19-60 years of age and neurological level AIS A-D (54% where incomplete at follow up), found an average loss of lean body mass corresponding to 20,5 and 15, 1% in the lower extremities and trunk respectively during the first year after injury. The course among people with SCI during and after discharge from the primary rehabilitation in Denmark is not known. BMI increases gradually, and especially during the first years after discharge from the primary rehabilitation. A Dutch prospective cohort study found that BMI increased gradually with a prevalence of overweight of 28 % during the primary rehabilitation and 54 % at follow up 5 years after discharge [7]. Similar inventories do not exist for people with SCI in Denmark. Obese people with SCI achieve a lower level of functioning during primary rehabilitation than people with normal weight [8], and more knowledge about prevention, treatment and managing overweight among people with SCI is warranted among health care professionals in the clinical setting. [9]. Overweight in people with SCI is associated with increased risk of depression, while physical activity may contribute to a decreased prevalence of depression and increased quality of life [10, 11]. The relationship between these variables in a Danish setting is not known.

Impact of physical activity on health and fitness

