Hypothesis

Targeted patient education in the form of "Strategic patient education" ¹ in relation to an interdisciplinary, multimodal and patient activating intervention at Rigshospitalet, Clinic for Spinal Cord Injuries (CSCI), is expected to contribute to a decrease of cardiovascular risk factors and maintenance of PA and healthy diet after discharge from the primary rehabilitation.

Purpose

The aim of this Ph.D project is to get an overview of the course of BMI among newly injured people with SCI in Denmark which serves as a historic control in conjunction with a systematic multimodal, intervention study, adapted to a Danish national setting with the aim of reducing cardiovascular risk factors and facilitating PA and healthy diet among all newly injured people with SCI during the primary rehabilitation and after discharge.

Designs (Design description for each sub study).

Sub study 1. Prospective representative longitudinal national survey of Body Mass Index.

Sub study 2. An interdisciplinary multimodal longitudinal controlled intervention study

[figure not shown]
Sub study 3. Test- retest reliability of VO2 peak

Sub study 4. Test-retest reliability of a multi sensor accelerometer.

Methods

¹ Defined as face-to-face interaction between the patient and health care professionals in order to facilitate the patients skills working towards a goal, that requires active patient participation related to decisions for one self and adherence to these. (See description under subproject 2)

Timeline for the project and used outcome measures

Usual rehabilitation today

Usual care during primary rehabilitation today before the intervention study (sub study 2), consists of interdisciplinary rehabilitation provided by doctors, nurses, physio- and occupational therapists, psychologist and social workers with every single profession contributing with their expertise.

According to the masterplan for patient care ("Patientforløbsbeskrivelsen" at Clinic for Spinal Cord Injuries (CSCI)) the patients neurological status (ISNCSCI), level of functioning (SCIM III), bowel and bladder function, cardiovascular and pulmonary function, medication, and psychological state is assessed at admission to CSCI. Non-SCI specific nutritional screening, assessment of body weight and screening for health related outcomes (diet, smoking, alcohol and exercise) is performed as well, but without a systematic approach and follow up.

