Although health promotion related to weight, diet, smoking, alcohol intake and physical activity is part of the usual rehabilitation in CSCI, a systematic approach, follow up and feedback is not provided. Assessment of metabolic profile, body composition and physical capacity is not part of the usual care. In the masterplan for patient care at CSCI, health promoting initiatives are described as "communication and conversation with a health promoting purpose with the patient on a daily basis". How the communication is carried out in practice, and whether some health care professionals have a particular responsibility or expertise related to certain aspects of health promotion eg. based on tests or assessments of health, is unclear and not described in detail. A well described and systematic approach related to health care promotion may ensure that all patients at CSCI receive information and knowledge related to health promotion and the risk of cardiovascular disease.

Sub projects

The project consists of a prospective national survey in collaboration with Spinal Cord Injury Centre of Western Denmark and an intervention at CSCI (see the timeline), which results in 4 sub projects

Sub project 1. Prospective representative national survey of Body Mass Index.

This study includes all patients with a new SCI hospitalized at CSCI or Spinal Cord Injury Center of Western Denmark during a period of 9 months whereby 100 patients are expected to participate. On the basis of usual rehabilitation today, data concerning BMI, level of functioning (SCIM III) and neurological status (ISNCSCI) are collected at admission and discharge. At CSCI BMI is collected every 6 weeks. Also the data for quality of life (QoL SCI), depression (PHQ-2), PA (LTPAQ-SCI) and self-assessed ability to be physically active (ESES) will be collected during this period and at follow up 6 months after discharge. A VO₂peak test at discharge is performed and in some patients measurements of accelerometry (AH) will be performed. Patients with a new SCI who are admitted for rehabilitation several months after the time of injury are also included in the prospective survey. Therefore the data for BMI at the time of injury is collected for all patients at admission to primary rehabilitation from both the patient journal and also by asking the patient about weight and height at the time of injury. Data from this subproject serves as a historic control in the Ph.D project.

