Sub project 2. A systematic interdisciplinary multimodal intervention which, as a part of usual care, facilitates PA, healthy diet and maintenance after discharge through strategic patient education, with the aim of decreasing cardiovascular risk factors.

This pre- post study includes all patients with a new SCI who are admitted at CSCI during a period of 12- 18 months including follow up. Complete data sets from admission to follow up is expected for approximately 50-60 patients during this period. The multimodal, interdisciplinary, patient activating and patient supportive intervention will be a part of usual care during the project period, and all newly injured patients will receive all the multimodal components, or parts of them, dependent on eg. the level of injury. Rehabilitation of the physical level of functioning and physical capacity will take place unchanged as usual.

A central part of the intervention is to create a uniform and systematic approach when the patients receive information and instructions about cardiovascular risk factors, PA and a healthy diet through targeted strategic patient education, which includes targeted, individualized and systematic, face- to-face interaction between patients and health care professionals, while working towards, and improving a specific health related outcome through adherence to the working processes, medicine and lifestyle. The concept has been used previously for patient education and prophylaxis of catheter related sepsis [44]. Strategic patient education is carried out by all the health care professions in different settings with a focus on clarifying the importance of PA and a healthy diet. This will take place during the individual functional training and rehabilitation in general, and in conjunction with feedback about outcome measures and tests with subsequent instructions. Strategic patient education will also be integrated as a concept in the education of the interdisciplinary health care professionals and mentors with a SCI, as they will be implementing the content of the education into a daily clinical setting.

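### Body composition, metabolic profile and diet have no listed historic-control values, so for these secondary outcomes sub study 2 is an uncontrolled before-after comparison under a controlled label

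*Protocol*

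**What the plan says.** The Designs section introduces the intervention study as "Sub study 2. An interdisciplinary multimodal longitudinal controlled intervention study". The description of sub project 2 uses another label: "This pre- post study includes all patients with a new SCI who are admitted at CSCI during a period of 12- 18 months including follow" (the sentence continues). The hypothesis is that the education programme "is expected to contribute to a decrease of cardiovascular risk factors and maintenance of PA and healthy diet after discharge from the primary rehabilitation".

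The historic control is sub project 1. Its listed data are BMI, SCIM III, ISNCSCI, QoL SCI, PHQ-2, LTPAQ-SCI, ESES, VO2peak at discharge, and accelerometry in some patients. The section on usual rehabilitation adds: "Assessment of metabolic profile, body composition and physical capacity is not part of the usual care". Diet is screened in usual care, but not systematically.

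Under sub project 2, measuring body composition, metabolic profile and diet is described as part of the intervention. The Statistics section gives a paired t-test as the analysis of change over time. Under Publication of results, the preliminary title of paper 2 begins "Effects of a Systematic and Interdisciplinary, Multimodal and Patient Engaging Intervention on" and goes on to name metabolic markers, body composition and diet among its outcomes.

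The background on the course of overweight describes change without any intervention: "Body fat and body weight also decreases in the acute phase, before increasing in the subacute phase". It also cites a longitudinal study that "found an average loss of lean body mass corresponding to 20,5 and 15, 1% in the lower extremities and trunk respectively" in the first year after injury.

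**The concern.** The label *controlled* and a title announcing effects tell the reader that change in these outcomes is judged against a comparison group. For DEXA, metabolic profile and diet no control values are listed, so only the within-patient change is available. That change mixes any intervention effect with the natural course after a new injury and with usual rehabilitation.

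The error can go either way. A favourable natural course would be published as benefit, and an unfavourable one could cancel a real benefit. An analysis plan cannot repair this, because no method can use control values that were not collected.

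**Working it through.** The Protocol gives no power, alpha, effect size or SD, so it has no figure to reproduce. The check has two steps.

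**Step 1. Match each sub study 2 outcome to the sub project 1 data list.**

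| Outcome in sub study 2 | Control data listed in sub project 1 |
|---|---|
| BMI, SCIM III, ISNCSCI | Admission and discharge (BMI also every 6 weeks at the Clinic for Spinal Cord Injuries, CSCI) |
| QoL SCI, PHQ-2, LTPAQ-SCI, ESES | During the stay and at 6-month follow-up |
| VO2peak (primary) | Discharge only, confirmed under Recruitment of participants |
| Accelerometry | Sub-sample only |
| Body composition (DEXA) | None |
| Metabolic profile (CRP, BP, lipids, HbA1c) | None |
| Diet (NORMON) | None |

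The background names six cardiovascular risk factors as examples: dyslipidemia, vascular inflammation, insulin resistance, type 2 diabetes, hypertension and overweight. Of these, only overweight has listed control data, through BMI. Of the two behaviours in the hypothesis, physical activity has control data and healthy diet has none.

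The proof is this list. The sentence on usual care is not enough by itself, because it also puts physical capacity outside usual care and VO2peak is nevertheless collected in sub project 1.

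**Step 2. Illustrate what a paired t-test shows when the intervention does nothing.**

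Inputs: n = 40 to 60 (Statistics; sub project 2 expects 50 to 60 complete data sets). Assumptions: two-sided alpha 0.05, and a natural change of d = 0.2, 0.3 or 0.5 SD of the paired differences.

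The test statistic follows a noncentral t distribution with n − 1 degrees of freedom and noncentrality d × √n. The probability of significance is P(|T| > t(0.975; n − 1)).

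Noncentrality:
- n = 40, √40 = 6.325: 1.26, 1.90, 3.16
- n = 50, √50 = 7.071: 1.41, 2.12, 3.54
- n = 60, √60 = 7.746: 1.55, 2.32, 3.87

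| n | d = 0 | d = 0.2 | d = 0.3 | d = 0.5 |
|---|---|---|---|---|
| 40 | 0.05 | 0.24 | 0.46 | 0.87 |
| 50 | 0.05 | 0.28 | 0.55 | 0.93 |
| 60 | 0.05 | 0.33 | 0.63 | 0.97 |

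Even a small natural change makes significance far more likely than the nominal 0.05. The result says that something changed. It does not say why.

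**The case against.** **One sentence points the other way.** The Outcome measures section opens by saying that every outcome is collected at all three time points and exempts no cohort. Read alone, it would give the control cohort DEXA, blood and diet data. It cannot settle the matter, because the sub project 1 list and the recruitment section contradict it for VO2peak. It is a conflict to reconcile. The timeline figure is missing from the text at hand and may show outcomes by cohort.

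**Much is already open.** The study is also called pre-post, the Purpose describes the historic control in terms of BMI, the affected outcomes are secondary, and the paper titles are preliminary. This stands and limits the weight of the point. It does not remove the conflict between the two labels or the effect wording for exactly these outcomes.

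**The document is headed for sub study 1.** True, but it describes the whole project, and what sub study 1 collects decides what sub study 2 can be compared with.

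**Stronger readings that fail.**
- A reader might infer that the study can show no effect on any risk factor in its hypothesis. It does not follow: overweight is a named risk factor and BMI has control data, inactivity and weight gain are the stated focus, and physical activity has control data to 6 months.
- A reader might also put the cited lean-mass losses of 20.5% and 15.1% into the paired test and conclude that a false benefit is almost certain. Those figures are regional and cover the first year after injury, whereas measurement starts 1 to 2 weeks after admission to rehabilitation, for some patients months after injury. No SD is given. A loss of lean mass is also adverse, so it illustrates masking of a benefit.

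**Conclusion.** The point holds for three groups of secondary outcomes: body composition, metabolic profile (lipids, HbA1c, CRP, BP) and diet. On the sub project 1 list they have no control values, so for them sub study 2 is an uncontrolled before-after study, and neither the label *controlled* nor effect wording is supported. The point does not extend to BMI, SCIM III, QoL SCI, PHQ-2, LTPAQ-SCI or ESES. VO2peak can be compared between cohorts at discharge only.

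The probabilities of 0.24 to 0.97 rest on an assumed alpha and assumed natural changes of 0.2 to 0.5 SD of the paired differences. The Protocol supports natural change in body fat, weight and lean mass, but gives no such figures for lipids, HbA1c, CRP, blood pressure or diet. The conclusion about attribution does not depend on the exact values.

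**What to change.** - In the design statement, the hypothesis and the title of paper 2, state that DEXA, metabolic profile and diet are reported as course over time, without attributing change to the intervention.
- Use *controlled* and effect wording only for outcomes with control data from CSCI, and only on the basis of a comparison between the cohorts. The Statistics section currently names only the within-patient test for change. For VO2peak the comparison is possible at discharge only.
- Reconcile the general sentence under Outcome measures with the sub project 1 list and the recruitment section, so that it is clear which outcome is collected in which cohort and when.

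The change is wording only. Its price is a less favourable claim for the metabolic, body-composition and diet outcomes.

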Data from the patient journals in Epic and the different outcome measures used, is stored in a web based database (Redcap) which is created by the regional Centre for IT, Medico and Telephony (CIMT), with limited access and ID- code, to which pseudo anonymized data is transferred directly,

or via an encrypted USB-stick. An identification list is stored in a locked cabinet at CSCI, local 3403.

Data is stored until December 31, 2027 after which paper material is shredded and data files are deleted.

Statistics

The intervention study and follow up is performed as a pragmatic study and includes, with a few exceptions, all newly injured patients with SCI admitted to primary highly specialized rehabilitation at CSCI. Patients will be included during a time period of 18 corresponding to approximately 40 – 60 patients. Due to the rareness of the morbidity a power calculation is not performed for the primary outcome prior to the intervention, but it is assumed that the total participant number in the intervention and in the historic control cohort, will be comparable to the existing scientific literature.

Numeric continuous data collected at admission, discharge and follow up is reported descriptively as mean and standard deviation together with 95% confidence intervals, or as median, upper and lower quartile as well as interquartile range. Changes over time is reported on the basis of paired t-test. In subproject 3 and 4 the reliability of the outcome measures is analyzed by paired t-test, Pearsons product moment correlation and coefficient of variation or Intraclass correlation coefficient between the test- retest sessions.

Participants, inclusion- and exclusion criteria

Inclusion criteria: All newly injured patients within the previous 12 months, with a SCI and admitted at CSCI are included, regardless of age, neurological level of lesion and completeness of the injury. In subproject 1 all newly injured people with SCI admitted at VCR are also included. Patients under the age of 18 will participate if informed consent is retrieved from their parents.

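### The historic control is defined as the whole two-centre survey, but the intervention is given at one centre, so for BMI and SCIM III a difference between cohorts would partly reflect centre

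*Protocol*

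**What the plan says.** **Control cohort.** Sub project 1 is recruited at two centres over nine months, and its expected size is 100: "This study includes all patients with a new SCI hospitalized at CSCI or Spinal Cord Injury Center of Western Denmark during a period of 9". The participants section repeats the point: "In subproject 1 all newly injured people with SCI admitted at VCR are also included". So does Recruitment of participants: "All newly injured patients who are admitted for rehabilitation at VCR in the same period are recruited for subproject 1". VCR is read here as the abbreviation for the western Danish centre. No split of the 100 patients by centre is given.

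**Role as control.** The description of sub project 1 ends with "Data from this subproject serves as a historic control in the Ph.D project". The Purpose describes "the course of BMI among newly injured people with SCI in Denmark which serves as a historic control". Neither statement is limited to CSCI, and no other section limits it.

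**Intervention cohort.** Sub project 2 "includes all patients with a new SCI who are admitted at CSCI". VCR patients have no route into it.

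**Data by centre.** Recruitment of participants names BMI, SCIM III and ISNCSCI as the data taken at VCR. It describes VO2peak in sub project 1 as a CSCI measurement made at discharge, and it describes the questionnaires as handled by the Ph.D student at CSCI.

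**Analysis.** The Statistics section gives descriptive summaries and paired t-tests for change over time. It sets out no test between cohorts and no centre factor.

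**The concern.** A historic control is informative to the extent that the setting stays the same and only the period and the programme change. Here the setting changes too. For BMI and SCIM III the control would come from two centres and the intervention cohort from one. Any difference between the centres in catchment, case mix or usual care would then be carried into the contrast that is read as the programme's effect.

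The protocol gives no basis for treating the centres as interchangeable. Its account of usual care rests on CSCI's own plan for patient care, and nothing comparable is given for VCR. Six-weekly BMI collection is specified for CSCI only.

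At stake is the interpretation of secondary outcomes. A BMI difference in either direction could be credited to the programme when part of it is a difference between hospitals. Recruiting more patients at both centres in the same proportion would not shrink that part. The two-centre population does suit the national survey; the difficulty arises only when the same population also serves as the control.

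**Working it through.** The protocol states no figure for this comparison, so there is none to reproduce. The check is structural, with an illustration of size.

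**1. The populations side by side**

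| | Control (sub project 1) | Intervention (sub project 2) |
|---|---|---|
| BMI, SCIM III, ISNCSCI | CSCI and VCR | CSCI |
| VO2peak, questionnaires | CSCI, as described under recruitment | CSCI |

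**2. Form of the bias.** Let w be the VCR share of controls, and let μC and μV be the mean outcomes under usual care at CSCI and VCR. The control mean is (1 − w)μC + wμV. Suppose the programme has no effect and nothing changes over calendar time. The intervention-minus-control difference is then

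μC − [(1 − w)μC + wμV] = w(μC − μV).

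So bias = w × d, where d = μC − μV. It can have either sign, and it is zero if the centres do not differ.

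**3. Range for w.** The protocol does not give w. A rough range follows from scaling CSCI numbers to the survey's 9 months and subtracting from 100, assuming constant admissions:

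- Statistics section, 40-60 patients over 18 (no unit printed; months assumed): 40 × 9/18 = 20 to 60 × 9/18 = 30 CSCI patients, so w is about 70-80%.
- Sub project 2, 50-60 complete data sets over 12-18 months: 50 × 9/18 = 25 to 60 × 9/12 = 45, so w is about 55-75%.
- The same figures if six-month follow-up leaves only 6 months of a 12-month period for enrolment: 50 × 9/6 = 75 to 60 × 9/6 = 90, so w is about 10-25%.

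The second and third lines count complete data sets, which may understate CSCI admissions and so overstate w. The range carried forward is 10-80%.

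**4. Range for d.** The protocol has no information on d. A difference of 0-1.0 kg/m2 in BMI change is assumed, with zero included because nothing shows that the centres differ.

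| w | d = 0 | d = 0.5 | d = 1.0 kg/m2 |
|---|---|---|---|
| 0.1 | 0 | 0.05 | 0.1 |
| 0.5 | 0 | 0.25 | 0.5 |
| 0.8 | 0 | 0.40 | 0.8 |

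**5. Precision lost by using CSCI controls only.** Minimum detectable difference at 80% power, two-sided 5%, with 50 intervention patients and outcome SD = 1: (1.960 + 0.842) × √(1/n + 1/50), where n is the number of controls.

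- n = 100 (both centres): 2.802 × 0.173 = 0.49 SD
- n = 50: 2.802 × 0.200 = 0.56 SD
- n = 30: 2.802 × 0.231 = 0.65 SD
- n = 20: 2.802 × 0.265 = 0.74 SD

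The CSCI-only values of n are assumptions. The values 20 and 30 match the first line of step 3.

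**The case against.** The strongest reply is that the protocol never sets out the comparison in question. Sub project 2 is called a pre-post study and the stated tests are within-patient. A SAP, which is not at hand, might choose the control patients for each outcome. That stands in part: no planned test can be called invalid. But the protocol also lists sub study 2 as a controlled study and twice says what its control is. Which patients form the control is a design statement already made, and a SAP restricting it to CSCI would depart from that statement.

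Three stronger readings might be inferred, and the protocol does not support them:

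- *Every BMI or SCIM III comparison is confounded by centre.* It is not. Patients can be separated by centre, and a comparison using only CSCI controls avoids the problem. The protocol already accepts a subset of controls for one outcome, accelerometry.
- *The primary result is biased by centre.* VCR is not named as a source of VO2peak or questionnaire data, so those comparisons are not reached.
- *The bias is known to be material.* Nothing shows that case mix or care differs between the centres. If they do not differ, the bias is zero.

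It is also fair to say that BMI and SCIM III are secondary in sub project 2, that the preliminary title of its effects paper names neither, and that dropping VCR could leave few controls. These points limit how serious the matter is and argue against banning VCR data altogether. They do not justify leaving the two-centre definition in place.

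**Conclusion.** The point holds as a flaw in the definition of the control. As written, the historic control for BMI, SCIM III and ISNCSCI is a two-centre population set against a one-centre intervention cohort, which partly confounds centre with programme. It should be corrected, but it concerns secondary outcomes and does not touch VO2peak.

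The size cannot be determined from the protocol. The range of 0-0.8 kg/m2 for BMI rests on an assumed VCR share of 10-80% and an assumed centre difference of 0-1.0 kg/m2. It shows what could happen and is not an estimate. The structural finding needs neither assumption.

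**What to change.** In the Purpose and in the description of sub project 1, state that the control for the main comparison with sub project 2 is the sub project 1 patients admitted at CSCI. Keep VCR patients in the national BMI survey and report that survey by centre. If a pooled two-centre comparison is wanted, show it only as a sensitivity analysis labelled as such.

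This changes wording only; no data collection changes. The cost is fewer controls for BMI and SCIM III. With 50 intervention patients the minimum detectable difference rises from 0.49 SD to about 0.56 SD if 50 controls remain, or 0.74 SD if 20 remain. The protocol should therefore also give the expected CSCI number. The change removes the centre part of the bias by design. Confounding by calendar time, inherent in a historic control, remains and should be acknowledged.
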